7.1 AMENDMENT D

We will increase our accrual ceiling for several reasons. The initial sample size calculation was based on a non-inferiority analysis of ⁶⁸Gallium-DOTATATE PET/CT to octreoscan SPECT, the currently used imaging study to detect NETs. Our interim analysis in 50 patients shows that ⁶⁸Gallium-DOTATATE PET/CT is much more accurate than Octreoscan SPECT (overall accuracy of 78% for ⁶⁸Gallium-DOTATATE PET/CT; 60% for Octreoscan SPECT, 74% for triphasic CT scan% in a per patient analysis). Thus, the sample size calculation has been revised to determine if ⁶⁸Gallium-DOTATATE PET/CT is more accurate than CT scan. Based on the data collected, the difference in the diagnostic accuracy between these two imaging techniques is 4% and the proportion of discordant imaging results is 12%. In order to detect 5% difference between these two imaging techniques with 80% power and with 10% discordant rate, 295 patients are required. The comparison is based on McNemar's chi-squared test at the 5% significance level. Thus, we are increasing our accrual ceiling to 295 patients. In addition, in a per lesion analysis between the two imaging techniques (⁶⁸Gallium-DOTATATE PET/CT and triphasic CT), there were discordant results in 30 of the 50 subjects (in 26 patients, ⁶⁸Gallium-DOTATATE PET/CT found additional lesions, in 4 patients CT found additional lesions, 20 patients had concordant (positive or negative) results). Additional reasons to increase the accrual ceiling are: 1) the most accurate way to confirm the results and findings from ⁶⁸Gallium-DOTATATE PET/CT scan is to compare them to pathologic evaluation of resected tumors. Thus far, 21 of 84 subjects have been recommended to have surgical treatment because of metastatic disease detection on ⁶⁸Gallium-DOTATATE PET/CT, and 9 patients have had a surgical procedure with pathology confirming the results (all true positives). Therefore, in order to increase the power of this comparison, an increase in accrual would be necessary. 2) We have used a gamma probe for intra-operative detection of NETs, in two subjects the results were positive and in order to validate this technique, an increase in number of patients would be needed.

7.2 AMENDMENT H

The sub-aim of Aim 1 was to determine the accuracy of ⁶⁸Ga-DOTATATE to detect unknown primary NETs. However, the current study is under-powered to achieve the first aim in detecting a 20% difference in detection rate between the two imaging modalities (⁶⁸Ga-DOTATATE and CT scan). Of 290 patients accrued to the study, as of amendment G, twenty-one had unknown primary NETs. Under the current accrual trend, assuming a total of 25 patients in the entire cohort have unknown primary 40% of whom were identified by ⁶⁸Ga-DOTATATE. Assuming the proportion of discordant imaging result is 24%. The current study would have only 50% power to detect a 20% difference using McNemar's chi-squared test at the 5% significance level. In order to achieve 90% power, the number of patients with unknown primary NETs need be increased to 55 subjects total (34 excluding those already enrolled).

To date, 24 patients accrued in the current study, as of amendment G, underwent radio-guided surgery with a total of 56 lesions detected on histology. Based on the preliminary data, lesion-

Abbreviated Title: ⁶⁸Gallium Detecting Tumors

Version Date: 09/20/17

based detection rate of DOTATATE gamma probe and CT scan/operative visualization was 71% and 57%, respectively. Assume on average 2 lesions per patient are identified by histology. The variance of the difference in detection rate between the two imaging guided procedures is given by

$$\text{Var}(\hat{P}_1 - \hat{P}_2) = n^{-1}(V_1 + V_2)[1 + (k - 1)r_1] - 2n^{-1}r_2\sqrt{V_1 V_2}$$

$$= \frac{\sigma^2}{n}$$

, where $V_i = \frac{P_i(1-P_i)}{k}$, P_i = true detection rate(i=1 for DOTATATE gamma probe and i=2 for CT

scan), \hat{P}_i = estimated detection rate , k = number of lesions per patient on average, r_1 = inter-lesion correlation, r_2 = intra-lesion correlation between the , and n = number of patients. Based on prior studies, inter-lesion correlation arising from multiple lesions of the same patient is set at 0.2 and intra-lesion correlation between DOTATATE and CT is set at 0.5. With these values and assuming $P1=0.72$ and $P2=0.57$, $\sigma=0.40$. To achieve 90% power in detecting 15% difference in detection rate between the two imaging modalities, with $\sigma=0.40$ a total of 85 patients (including the 24 patients already enrolled) are required using a two-sided Z-test at the 5% significance level.

Therefore, we are increasing our accrual ceiling to 390 patients.

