7 STATISTICAL CONSIDERATIONS

The primary objective of this prospective study is to assess the diagnostic accuracy of the new imaging technique ⁶⁸Gallium-DOTATATE PET/CT scan for patients with NETs. Based on the existing literature, the rate of correct classification of this new imaging technique against the gold standard of Octreoscan SPECT is about 85% [46, 60]. Assuming that on average 2 lesions will be evaluated for each patient, and that classifications of the multiple lesions from the same patient are modestly correlated with a correlation coefficient set at 0.2, the sample size is determined to achieve a desired precision of the estimate of the proportion of correct classification measured by the width of the 95% confidence interval. A few scenarios of sample size and true rate of correct classification are considered and listed in the following table.

Number of patients	True proportion of correct classification	95% confidence interval
50	0.85	(0.77,0.93)
100	0.85	(0.80,0.90)
150	0.85	(0.81, 0.89)
200	0.85	(0.81,0.89)
50	0.87	(0.80,0.94)
100	0.87	(0.82,0.92)
150	0.87	(0.83,0.91)
200	0.87	(0.83,0.91)

If the true proportion of correct classification is 0.85, with 50 patients, the 95% expected confidence interval is (0.77, 0.93), and with 100 patients, the 95% expected confidence interval is smaller (0.80, 0.90). The confidence interval is shortened only slightly even if the sample size is doubled to 200. This is also the case when the true proportion of correct classification is 0.87. Even though there does not appear to be a big difference in the confidence interval for the estimated accuracy of ⁶⁸Ga-DOTATATE for the sample size of 50 patients as compared to 100 patients, based on the literature [61], less than 20% of the patients are expected to have negative NETs. As a result, with the total sample size of 50 patients, likely less than 10 patients would have negative NETs, which is too small to estimate the specificity with precision. Hence the study is targeted at a sample size of 100 patients resulting in a 10% width of the 95% expected confidence interval for the estimate of the correct classification rate of ⁶⁸Ga-DOTATATE. As such, the study has an adequate size to estimate both the correct classification rate and sensitivity and specificity.

Studies have shown specificities for ⁶⁸Ga-DOTATATE PET/CT as high as 90% for primary and metastatic NETs [42, 60]. Patients included in the protocol will have yearly follow-up with

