7.3 DETAILED ANALYSIS

We recently performed an analysis of the detection rate of the 3 imaging modalities in the first 131 patients enrolled in the study for known or suspected gastrointestinal and pancreatic neuroendocrine tumors. Lesions detected on any of the 3 imaging modalities were defined as the denominator. ⁶⁸Gallium-DOTATATE detected 95.1% of lesions compared to Octreoscan SPECT, which only detected 30.9% of lesions ($p<0.0001$). Furthermore, in four out of 14 patients, ⁶⁸Gallium-DOTATATE PET/CT found a previously unknown primary tumor not detected by Octreoscan SPECT. Twenty-five patients underwent surgical resection for their primary tumors and/or metastases. An analysis of imaging concordance with histopathology showed that ⁶⁸Gallium-DOTATATE PET/CT found true-positive lesions 63.7% (72 out of 113 lesions) compared to 22.1% (25 out of 113 lesions) for Octreoscan. In assessing the impact of ⁶⁸Gallium-DOTATATE PET/CT on clinical management, ⁶⁸Gallium-DOTATATE PET/CT detected additional lesions in 93 out of the 131 patients (71.0%) compared to Octreoscan SPECT. Forty-four out of the 93 patients with additional lesions were found to have metastatic disease. These additional findings led to a change in management in 43 out of the 131 (32.8%) of patients. Given the clear imaging superiority of ⁶⁸Gallium-DOTATATE PET/CT to Octreoscan, we will no longer perform Octreoscan in patients being enrolled and will compare its accuracy to CT/MRI scanning. This will result in lower radiation exposure to subjects and reduced cost.

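### The unknown-primary comparison in section 7.2 is powered on raw detection rate while its stated aim is accuracy, so wrong-site calls can be credited and PET favoured if it makes more of them than CT

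*Combined protocol and SAP*

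**What the plan says.** Section 7.2 (Amendment H) opens its first calculation with the aim: "The sub-aim of Aim 1 was to determine the accuracy of" PET for unknown primary tumours. The quantity it then powers is a detection rate, the target being "detecting a 20% difference in detection rate between the two imaging modalities". PET successes are described by what PET named: "assuming a total of 25 patients in the entire cohort have unknown primary 40% of whom were identified by" PET. The other inputs are 24% discordant results and McNemar's "chi-squared test at the 5% significance level". The section puts power at 50% with 25 patients and asks for 55 patients to reach 90%. It gives no reference standard for the primary site and no rule for a call that proves wrong.

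The gamma-probe calculation in the same section does count lesions found on histology, and section 7 makes histology the standard for that comparison.

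Section 7.3 computes a detection rate whose denominator is every lesion seen on any of three scans (95.1% for PET). It reports agreement with histology as a separate analysis (72 of 113 lesions, 63.7%). It also says that in 4 of 14 patients PET "found a previously unknown primary tumor not detected by Octreoscan SPECT", without saying whether those sites were confirmed.

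Section 7 has two general safeguards: yearly conventional imaging, and histopathology in patients who have surgery (10-30% expected). It cites PET specificity "as high as 90% for primary and metastatic NETs".

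**The concern.** In a patient whose primary is unknown, a scan can miss the primary or name the wrong site. A test on raw detection penalizes only the miss. A focus called primary that is really a metastasis, or not tumour at all, enters the table the same way as a correct localization.

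A false call matters most when the other scan names nothing, because it then lands in a discordant cell, and McNemar's test uses only those cells. A scan that names more sites can therefore win without localizing more primaries. A significant result would show that PET names a primary more often than CT. It would not by itself support the accuracy statement for which section 7.2 added the comparison, and which forms part of the primary objective in section 1.1.1.

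**Working it through.** **Cells implied by the plan.** Let b be the share of patients with a PET-only call and c the share with a CT-only call. From section 7.2, b + c = 0.24 and b − c = 0.20, so b = 0.22 and c = 0.02. With PET at 40%, both scans are positive in 40 − 22 = 18%, and CT is at 18 + 2 = 20%.

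**The plan's own figure.** Sidedness is not stated and is taken as two-sided 5%.
- Unpooled formula: n = (1.960 + 1.282)² × (0.24 − 0.20²) / 0.20² = 52.5, so 53.
- Null/alternative variance formula: n = (1.960√0.24 + 1.282√0.20)² / 0.20² = 58.8, so 59.
- Exact enumeration of the uncorrected McNemar chi-squared test at n = 55, b = 0.22, c = 0.02: power 92.3%.

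The stated 55 for 90% power is reproduced within the spread of standard methods. The stated 50% at 25 patients is not matched by the same enumeration, which gives 60.1%. That is a separate matter and does not affect this point.

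**No true advantage, with false calls added.** The test rejects when (B − C)² / (B + C) > 3.84, where B and C are the PET-only and CT-only counts. The figures below are exact probabilities of rejecting in PET's favour at n = 55.

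Assumptions, none of them in the documents as wrong-primary rates:
- True discordance is 2% each way; 2% is the CT-only cell implied above.
- PET adds 8 points of false primaries. This is 10% (from the cited 90% specificity) of the 80% of patients whose primary is not truly seen (100 − 20).
- False calls fall in patients for whom the other scan names no site.
- CT adds 0 to 8 points of its own.

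| False CT calls | b | c | PET declared better |
|---|---|---|---|
| 0 points | 10% | 2% | 40.6% |
| 2 points | 10% | 4% | 19.9% |
| 4 points | 10% | 6% | 9.6% |
| 6 points | 10% | 8% | 4.6% |
| 8 points | 10% | 10% | 2.2% |

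With CT at 0 and PET's false calls varied instead, the probability is 0.9% at 0 points, 21.9% at 5, 52.9% at 10 and 92.3% at 20. At 20 points the table is the planned 22%/2% split, so the test cannot tell that case from a real 20-point gain.

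**Power if only correct primaries count.** Let s be the share of the 22% PET-only calls that are wrong (assumed). The true difference is 0.22(1 − s) − 0.02.
- s = 20%: 0.176 − 0.02 = 15.6 points; power at 55 is 80.6%.
- s = 30%: 0.154 − 0.02 = 13.4 points; power at 55 is 71.4%.
- s = 50%: 0.110 − 0.02 = 9.0 points; power at 55 is 46.8%.

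**The case against.** No sentence in the plan says that a wrong focus counts as a success. The sub-aim is accuracy, the probe calculation in the same section is anchored to histology and calls its parameter the true detection rate, and a tumour that was found can be read as a real tumour. A reader might infer that the plan deliberately scores wrong sites in PET's favour. The documents do not support that; they leave the term open. But section 7.3 uses the same term for anything seen on a scan, so a correct-site meaning cannot be assumed.

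The protocol does value confirmation. Section 1.2 plans correlation with anatomic imaging and pathology. Section 7.1 calls pathology the most accurate check and reports 9 operated patients, all true positives. Section 7.3 includes resected primaries, so pathology can bear on the primary site. These provisions reduce the concern for operated patients, but none of them defines the outcome of this test. The text of section 3.2 on follow-up was not available for this review and is not taken as silent.

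A reader might also take 41% as the test's false-positive rate. It is not. It requires PET to make 8 points of false calls and CT none. With equal false calls, the chance of a PET-favouring result stays near 2%. The 10% input is a borrowed general specificity, not a rate of naming the wrong primary, and the 20-50% shares of wrong PET-only calls have no source in the documents.

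Finally, scoring every unconfirmed site as a failure would bring in verification bias. Few patients were expected to have surgery, follow-up is mainly conventional imaging, and CT is the comparator. This objection stands and shapes the remedy.

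**Conclusion.** The concern holds as a mismatch between aim and outcome. The sub-aim is accuracy, the powered quantity is a detection rate without a correctness requirement, and the test as written can credit wrong-site calls. A spurious PET advantage arises only if PET makes more wrong primary calls than CT. Its size cannot be fixed from the documents: at 8 points of false PET calls it runs from about 41% down to 2%, depending on CT's own false calls. The documents do not show that PET's advantage is false, or that PET makes more wrong calls than CT. What they do not support is reading a significant detection-rate result as evidence of better accuracy. The plan should be changed before that claim is made; confidence is medium because the wrong-call rates are unknown.

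**What to change.** In section 7.2:
- Base the accuracy claim on a McNemar comparison of correctly localized primaries. Accept histology or other confirmation obtained in care, or documented follow-up under a stated definition, and apply the same rule to both scans.
- Score refuted or wrong-site calls as not detected.
- Run the test with unconfirmed sites counted as not detected and again as detected, and present the two results as bounds. If both scans leave unconfirmed sites, add the two opposed scorings (PET's wrong with CT's right, and the reverse), because the first pair need not then contain the extremes of the difference.
- Report confirmed, refuted and unconfirmed sites for each scan.
- Keep the raw test, labelled as detection and not accuracy, and state that the 90% power at 55 applies to it alone.

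The cost is analysis-plan wording and use of pathology and follow-up data already collected; no new procedure is needed. Some sites will stay unverified, so the bounds may be wide. Power at 55 for the accuracy comparison falls, for example from about 92% to 81% or 71% if 20% or 30% of PET-only calls are wrong.

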1.1.2 Secondary Objectives

- To evaluate ⁶⁸Gallium-DOTATATE uptake in NETs and its association with tumor differentiation.
- To determine whether ⁶⁸Gallium-DOTATATE uptake value is predictive of tumor growth and/or disease progression.
- To determine the relation between somatostatin receptor status in tumor samples and ⁶⁸Gallium-DOTATATE uptake.
- To evaluate the feasibility of radio-guided surgery in NETs using ⁶⁸Gallium-DOTATATE.

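### Section 7.2: the printed inputs for the gamma-probe comparison give 75 patients, not the stated 85, and no inflation is stated

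*Combined protocol and SAP*

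**What the plan says.** The calculation is in section 7.2 (Amendment H). It starts from the 24 patients who, as of Amendment G, "underwent radio-guided surgery with a total of 56 lesions detected on histology". In those patients the lesion-based detection rate for "gamma probe and CT scan/operative visualization was 71% and 57%, respectively".

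The section then prints a formula for the variance of the difference between two paired, clustered detection rates. It sets two lesions per patient, an inter-lesion correlation of 0.2, an intra-lesion correlation between the two methods of 0.5, and true rates of 0.72 and 0.57. From these it reports a standard deviation of 0.40.

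The design target is worded "To achieve 90% power in detecting 15% difference in detection rate between the two imaging modalities", and the conclusion is "a total of 85 patients (including the 24 patients already enrolled) are required using a two-sided Z-test at the 5% significance level". The section closes with "Therefore, we are increasing our accrual ceiling to 390 patients".

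Section 1.1.2 lists the related aim as a secondary objective: "To evaluate the feasibility of radio-guided surgery in NETs using" the study tracer.

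**The concern.** Section 7.2 goes straight from the standard deviation to the total, and all the ingredients of a standard one-line formula are on the page. Those ingredients do not return the stated total. No dropout rate, non-evaluability rate or other inflation is given to bridge the difference.

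As a result, the number cannot be tied to a definite design. It may reflect a smaller difference than the one named, a higher power than the one named, or an allowance that was left out. These are different claims about what the comparison can show. The figure also appears to carry into the current accrual ceiling, although the text does not print that sum.

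**Working it through.** **Inputs, all from section 7.2.** P1 = 0.72, P2 = 0.57, k = 2 lesions per patient, r1 = 0.2, r2 = 0.5, difference 0.15, power 90%, two-sided 5% Z-test. The normal quantiles are 1.960 and 1.2816, which sum to 3.2415.

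**Step 1: reproduce the plan's standard deviation.** With V = P(1 − P)/k:

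- V1 = 0.72 × 0.28 / 2 = 0.1008
- V2 = 0.57 × 0.43 / 2 = 0.12255
- σ² = (V1 + V2)[1 + (k − 1)r1] − 2·r2·√(V1·V2) = 0.22335 × 1.2 − 0.11114 = 0.26802 − 0.11114 = 0.15688
- σ = 0.396, which rounds to the printed 0.40

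The plan's σ reproduces, so the formula has been read as intended.

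**Step 2: from σ to n.** The section writes the variance as σ²/n, so n = 3.2415² × σ² / difference².

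- Printed σ = 0.40: 10.507 × 0.16 / 0.0225 = 74.7, so **75**
- Unrounded σ = 0.396: 73.3, so 74
- Stated: **85**

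**Step 3: can rounding explain it?**

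- Any σ that prints as 0.40 (0.395 to 0.405) gives 72.9 to 76.6 at 15 points, so at most 77.
- The least favourable values that round to both printed figures, σ = 0.405 and 14.5 points, give 10.507 × 0.164025 / 0.021025 = 82.0, still short of 85.
- For 85 to be the 90%-power number at 15 points, σ would have to be 0.15 × √85 / 3.2415 = 0.427.

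**Step 4: what does lead to 85?** None of these routes is stated as the basis.

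| Route | Result |
|---|---|
| Preliminary rates 0.71 and 0.57, 14 points, unrounded σ = 0.398 | 10.507 × 0.15828 / 0.0196 = 84.9, so 85 |
| 14 points with the printed σ = 0.40 | 85.8, so 86 |
| Counts 40/56 and 32/56, the only counts out of 56 that round to 71% and 57%, if 56 is the denominator for both (14.29 points, σ = 0.397) | 81.1, so 82 |
| 75 with an unstated loss allowance | 1 − 75/85 = 11.8% gives exactly 85; 75/0.89 = 84.3, so 85 |
| 15 points, σ = 0.40, higher power | 83.9 at 93% power |

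**Step 5: what 85 patients deliver.** Power = Φ(difference × √n / σ − 1.960).

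- 15 points, σ = 0.40: Φ(3.457 − 1.960) = 93.3%
- 14 points, σ = 0.398: 90.0%
- 14 points, σ = 0.40: 89.7%
- Difference with 90% power at σ = 0.40: 3.2415 × 0.40 / √85 = 14.1 points

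By contrast, 75 patients would have 85.8% power at 14 points with σ = 0.40.

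**Step 6: link to the ceiling (a reconstruction).** Section 7.1 sets 295. Section 7.2 asks for 34 further patients with unknown primary (55 − 21) and, by subtraction, 61 further radio-guided patients (85 − 24). The sum 295 + 34 + 61 = 390 matches the new ceiling. It treats the two groups as separate additions, which the text does not say. With 75 in place of 85 the same sum gives 380.

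**The case against.** The strongest reply is that this is a wording slip of little consequence. The same paragraph prints 71% and 57%. Put through the printed formula at 14 points, those rates give 85 at the stated power. No other route gives 85 using only figures in the section; the allowance and the higher power are fitted backwards. On that reading the rates were restated as 0.72 and 15 points without rerunning the total. The direction is also safe under the printed assumptions, and using the observed 56/24 = 2.33 lesions per patient instead of 2 would lower the requirement further, to 69. The objective is secondary and concerns feasibility, no analysis depends on the number, and the link to the ceiling is inferred.

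Most of this stands, and it limits the point to a minor one. It does not remove it. The 14-point explanation is the most plausible but depends on carrying σ unrounded: the printed 0.40 gives 86, and the likely raw counts give 82. The sentence in the plan names 15 points and 0.40, and with those inputs the total is wrong as written. The safe direction also holds only if 85 radio-guided patients are actually enrolled.

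**Conclusion.** The concern holds, as a minor arithmetic correction. Under the printed inputs the requirement is 75 patients (74 with unrounded σ) against the stated 85, a gap of 10 to 11. This rests only on figures printed in section 7.2 and on the test named there. The origin of 85 cannot be settled from the text. If 85 such patients are enrolled and the printed assumptions hold, the comparison has slightly more power than claimed at 15 points. What is lost is the ability to reproduce the justification, not the adequacy of the sample.

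**What to change.** Make the inputs and the total agree in section 7.2. The simplest change keeps 0.72 versus 0.57, 15 points, σ = 0.40 and 85 patients, and replaces 90% power with about 93%.

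If another basis was actually used, state that instead:

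- **A 14-point target:** print P1 = 0.71, 14 points and σ = 0.398 with 85 patients at 90% power. σ has to be restated too, because 0.40 would give 86.
- **An allowance:** print 75 as the evaluable number and the loss rate that leads to 85.

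Changing the total to 75 is also arithmetically consistent with 15 points at 90% power. It is less attractive, because it would leave about 86% power at 14 points and, if the reconstruction is right, would lower the ceiling to 380.

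Separately, print the sum behind 390 and say whether the two added groups may overlap.

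The cost is one or two sentences. The simplest fix leaves 85 and 390 as they are, adds no patients and changes no analysis.

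### The 24 probe patients whose results informed the powered comparison are also counted in its 85-patient test, with no rule or adjustment, so the 5% level is not protected.

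*Combined protocol and SAP*

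**What the plan says.** Section 7 describes the gamma probe as a feasibility aim. It plans to set probe findings against pre-operative PET/CT and against visualization and palpation, with histology as the reference, and gives no power calculation. Section 7.1 (Amendment D) cites two positive probe cases and says that more patients are needed to validate the technique.

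Section 7.2 (Amendment H) turns this into a powered comparison. In 24 patients with 56 histologically detected lesions, the lesion-"based detection rate of DOTATATE gamma probe and CT scan/operative visualization was 71% and 57%, respectively". The design then takes 72% and 57%, with σ = 0.40, and states: "To achieve 90% power in detecting 15% difference in detection rate between the two imaging modalities", "a total of 85 patients (including the 24 patients already enrolled) are required using a two-sided Z-test at the 5% significance level".

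For unknown primaries, the same section says that the number of patients "need be increased to 55 subjects total (34 excluding those already enrolled"), so 21 of the 55 are patients already in the study.

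Neither Section 7 nor its amendments mention an alpha adjustment, a combination test, a rule for when to extend, or a separate analysis of patients enrolled later.

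**The concern.** Results by method were seen in 24 patients. The powered comparison, its comparator (CT is added to visualization here for the first time) and its effect size were then written down. The same 24 make up 24/85 = 28% of the final sample, which is to be tested as if nothing had been looked at. If the favourable result influenced the decision to run this test, a lucky early run carries into the final p-value, and the pooled estimate leans toward the early effect. A reader of a significant pooled result could not tell fresh evidence from carry-over.

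**Working it through.** **Inputs, all from Section 7.2.** P1 = 0.72, P2 = 0.57; k = 2 lesions per patient; inter-lesion correlation r1 = 0.2; intra-lesion correlation r2 = 0.5; two-sided 5%; 90% power; 15 points; 24 patients seen, 85 in total, so 61 new. Observed rates 71% and 57%, a difference of 14 points.

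**1. The plan's σ.** With Vi = Pi(1 − Pi)/k, σ² = (V1 + V2)[1 + (k − 1)r1] − 2·r2·√(V1V2).
- V1 = 0.1008 and V2 = 0.12255.
- σ² = 0.22335 × 1.2 − 0.11114 = 0.1569, so σ = 0.396. This agrees with the stated 0.40.

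**2. The plan's 85.** n = (1.960 + 1.282)²σ²/d².
- Stated inputs (σ = 0.40, d = 0.15): 10.507 × 0.16/0.0225 = 74.7, that is 75. The stated 85 does not follow.
- Observed rates 71% and 57% (σ = 0.398, d = 0.14): 10.507 × 0.1583/0.0196 = 84.9, that is 85.

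The stated total therefore fits the observed effect better than the stated target. This suggests, but does not prove, that it was computed from the interim result.

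**3. Where the 24 patients stand.** z1 = 0.14 × √24/0.40 = 1.71. Paired interim data are not given, so this rests on the plan's variance model; σ = 0.398 gives 1.72.

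**4. Pooled test given that start, with no true effect in the 61.** Let w = √(24/85) = 0.531. The pooled statistic is w·z1 + √(1 − w²)·X, with X standard normal.
- P(favours probe) = P(X > (1.96 − 0.531 × 1.715)/0.847) = P(X > 1.238) = 0.108.
- The nominal figure in that direction is 0.025. The chance of significance against the probe is below 0.001.

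**5. What the overall error depends on.** These are two-sided rates under no effect, from 4 million simulated trials, among the tests actually pursued:

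| Rule for pursuing the 85-patient test | Error |
|---|---|
| Always | 5.0% |
| Only if z1 > 0.5 | 6.8% |
| Only if z1 > 1.0 | 9.8% |
| Only if z1 > 1.5 | 14.5% |

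If only the sample size is re-set from the observed effect (caps from 85 to 400), the unconditional error is 5.5% to 6.0%.

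**6. Power with and without the 24.** Power = Φ(d√n/0.40 − 1.96).

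| n | d = 0.15 | d = 0.14 |
|---|---|---|
| 61 (new only) | 83% | 78% |
| 85 (pooled) | 93% | 90% |

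**7. Unknown primary, 34 new patients.** With the plan's 20% difference and 24% discordance, the McNemar formula gives Φ[(0.20√34 − 1.96√0.24)/√(0.24 − 0.04)] = Φ(0.46) = 68%. The exact test gives 59%. The same formula at 55 gives 88%, against the stated 90%.

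**The case against.** Reusing patients does not by itself inflate the error; a data-driven choice to go on does. There are signs that the probe work would have continued anyway. Section 7 already planned to count lesions found by probe against those found by visualization and palpation, and Amendment D asked for more patients when only two positive cases were in hand. The 11% is also conditional on one interim value, while 2.5% is an unconditional rate. All of this stands, and it rules out saying that the 5% level fails. It does not show that the level holds: the CT component and the formal sizing first appear next to the favourable result, and no rule is recorded.

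A reader might infer that the unknown-primary test has the same fault. The documents do not support that. Detecting unknown primaries is already in the primary objective (Section 1.1.1), and Amendment H justifies the increase by too few such patients. It reports no DOTATATE-versus-CT result in the 21. The 20% is a difference to detect and the 24% is introduced as an assumption. Nor could both be counts from those patients: 24% of 21 is five discordant patients, which allows a net difference of 1, 3 or 5 (4.8%, 14.3% or 23.8%), not 20%. No error rate can be given for that test.

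A reader might also see Amendment D's move to CT as comparator in the same light. Section 7.1 ties that move to the result against Octreoscan (78% versus 60%), not to a favourable result against CT.

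**Conclusion.** The point holds for the probe comparison. The same 24 patients supply the rates, inform the design and enter an unadjusted two-sided 5% test, and the plan records nothing that would protect that level. Given their result and no later effect, the pooled test would favour the probe about 11% of the time. This assumes the plan's variance model and is conditional on z1 = 1.71. The unconditional error lies between 5% and something higher, depending on an undocumented rule. Bias in the pooled estimate likewise depends on selection having taken place.

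For unknown primaries, only the reuse of 21 of 55 patients is established, which calls for transparency rather than a claim of inflated error.

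**What to change.** **Probe.** In Section 7.2, do one of the following:
- Base any 5%-level claim on the 61 patients enrolled after Amendment G, and report the pooled 85 as an estimate with confidence interval.
- Keep the pooled test, label its p-value exploratory, and show the 61 new patients beside it.

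Reconcile the stated 85 with the 15-point target, which gives 75.

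**Unknown primary.** Report the 34 new patients beside the pooled 55.

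**Cost.** Wording and one split of the data, with no added patients. Relying on the 61 lowers power from 93% to 83% at 15 points and from 90% to 78% at 14. The 34 unknown-primary patients alone have about 68%, so their result is a consistency check rather than a stand-alone test.
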